### Pseudocode for Tipping Point analysis:

- Define input dataset as the dataset of all subjects with a missing outcome.
- Define  $P_T$  as the proportion of subjects imputed as Event in the Lenzilumab + RDV.  $P_T$  will take values 1, 5, 10, 15, 20, 40%
- Define  $P_P$  as the proportion of subjects imputed as Event in the Placebo + RDV.  $P_P$  will take values 1, 5, 10, 15, 20, 40%
- For each combination of  $P_T$  and  $P_P$ , follow the below pseudocode to impute missing data and fit the final model to obtain odds ratio and its 95% CI along with the p-value.

```

Data imp_tipping_&pp._&pt. ;
  set input;
  subid=input(substr(usubjid,5,4),best12.);
  seed=645+subid;
  call streaminit(seed);
  pP= &pp.;
  pT= &pt.;
  do i=1 to 20;
    _imputation_ = i;
    If TRTVAR='Placebo + RDV' then      eventd29=rand("Binomial",pP,1);
    Else if TRTVAR='Lenzilumab + RDV' then eventd29=rand("Binomial",pT,1);
    output;
  end;
  drop p i;
run;

```

For each of the 20 imputed datasets, combine `imp_tipping_&pp._&pt.` with the dataset of all subjects with complete outcome data to obtain the final dataset `imp_tipping_final_&pp._&pt.`

### Odds ratios from logistic regression using multiple imputation for each scenario:

```

proc logistic data= imp_tipping_final_&pp._&pt. out=imp_parms_&pp._&pt. ;
  by _imputation_;
  class baseordscorevar (param=ref ref=5) basedexausevar (param=ref ref=no steroid
use) trtvar (param=ref ref=placebolabel);
  model eventd29 (event='1') = trtvar baseordscorevar basedexausevar age baseCRP;

```

```
run;

proc mianalyze data=parms_&pp._&pt. ;
  class baseordscorevar (param=ref ref=5) basedexausevar (param=ref ref=no steroid
use) trtvar (param=ref ref=placebolabel);
  modeleffects trtvar baseordscorevar basedexausevar age baseCRP;
  ods output parameterestimates=mianalyze_parms_&pp._&pt. ;
run;

data OR_&pp._&pt. ;
set mianalyze_parms_&pp._&pt. ;
  OR=exp(estimate);
  LCL_OR=exp(LCLMean);
  UCL_OR=exp(UCLMean);
run;
```

Repeat the above process for all combinations of  $P_T$  and  $P_P$  to obtain estimates and p-values for each scenario.

## 8.2. Key Secondary Efficacy Analyses

All analyses of key secondary endpoints on the ITT population outlined in Section 8.2.1, Section 8.2.2, Section 8.2.3 and Section 8.2.4 will be repeated for the mITT analysis population. For brevity, only the ITT analyses are described in the text and presented in output shells. The mITT analyses and their output will follow exactly what is provided for their ITT counterparts.

### 8.2.1. Time to Mechanical Ventilation or Death Up to and Including Day 29 for Primary Endpoint Subgroup and All Subjects in ITT Population

The time to mechanical ventilation or death up to and including Day 29 will be defined as the elapsed time (in days) from Study Day 1 to date of invasive mechanical ventilation/ECMO or death. For the primary analysis of this endpoint, all subjects lost to follow-up or terminated early prior to death or progression to invasive mechanical ventilation will be considered non-events and censored at the date of their last observed assessment. As sensitivity analysis of this endpoint, any subjects that are lost to follow-up or terminated early prior to death or progression to mechanical ventilation and were discharged to a location other than LTAC, hospice care or other hospital, or progress to invasive mechanical ventilation/ECMO or death after Day 29 will be considered non-events and censored at Day 29 while subjects that are lost to follow-up or terminated early before Day 29 and before progression to invasive mechanical ventilation/ECMO or death and were either still hospitalized or discharged to LTAC, hospice care or other hospital at their last assessment will be considered non-events and censored at the date of their last observed assessment. If it is learned that a subject who terminated early had subsequently received ventilation or died prior to Day 29, then the subject will be classified as having the event. Subjects who complete follow-up without an event will be censored at the date of their expected Study Day 29 visit. Events that occur after Day 29 will be censored at the expected Study Day 29 date.

Table 7 will present median time to event along with corresponding 95% confidence intervals for each Lenzilumab + RDV long with the hazard ratio estimate and p-value from a Cox proportional hazards model for subjects in the primary subgroup. Restricted mean survival time estimates (RMST) which do not rely on the proportionality assumption will be provided for each treatment group and actual baseline ordinal score stratum as well as the difference in restricted mean recovery time between treatment groups within each of the

baseline ordinal score strata for the primary subgroup ([Table 9](#)). For both the Cox proportional hazards model and the RMST method, tied event times will be handled using the Efron method.

Kaplan-Meier curves for each Lenzilumab + RDV will be presented and supplemented with the hazard ratio estimate, p-value, and the number of subjects at risk in each Lenzilumab + RDV Study Day (not necessarily actual Study Days 1, 3, 5, 8, 11, 15, 22, 29) ([Figure 1](#)). A forest plot will be generated to display 95% CIs for hazard ratios from each of the subgroup analyses ([Figure 5](#)). These analyses will also be repeated for all subjects in the ITT population and results will be reported in [Table 8](#), [Figure 2](#), and [Figure 6](#).

Refer to [Table 1](#) for a list of covariates and subgroup analyses for this endpoint. Refer to [Table 2](#) for imputation methods to be applied to this endpoint.

### **8.2.2. Time to Sustained Recovery Up to and Including Day 60 for Primary Endpoint Subgroup in the ITT Population**

Recovery will be defined as having a value of 1, 2, or 3 on the clinical status 8-point ordinal scale or discharge from the hospital to a location other than LTAC, hospice care, or other hospital. The time to sustained recovery will be defined as the elapsed time (in days) from Study Day 1 to the day prior to the earliest recorded day at which a subject reaches recovery and doesn't worsen (ordinal score  $> 3$ ) up to and including Study Day 60. This analysis will be conducted on the ITT population for those subjects who at baseline have a clinical status score of 5 or 6, CRP $<150$  mg/L, and age $\leq 85$  years. For the primary analysis of this endpoint, all subjects lost to follow-up or terminated early prior to recovery will be considered not recovered and censored at the date of their last observed assessment, regardless of their discharge status. As sensitivity analysis of this endpoint, any subjects that are lost to follow-up or terminated early prior to recovery and were discharged to a location other than LTAC, hospice care or other hospital will be considered recovered by study Day 60 with a time to recovery of time of discharge or time of first score of 1, 2, or 3, whichever comes first, while subjects that are lost to follow-up or terminated early before Day 60 before recovery, were still hospitalized or were discharged to LTAC, hospice care or other hospital at their last assessment will be considered not recovered and censored at the date of their last observed assessment.

Refer to [Table 1](#) for a list of covariates and subgroup analyses for this endpoint. Refer to [Table 2](#) for imputation methods to be applied to this endpoint.

The primary analysis time to sustained recovery up to and including Study Day 60 conducts a score test to compare treatment to control up to and including Study Day 60. The treatment median survival time, confidence intervals and p-value from the score test will be presented ([Table 10](#)). Restricted mean recovery time estimates will be provided for each treatment group and actual baseline ordinal score stratum as well as the difference in restricted mean recovery time between treatment groups within each of the baseline ordinal score strata ([Table 12](#)).

Kaplan-Meier curves for each Lenzilumab + RDV will be presented and supplemented with the hazard ratio estimate, p-value, and the number of subjects at risk in each Lenzilumab + RDV Study Day (not necessarily actual Study Days 1, 3, 5, 8, 11, 15, 22, 29, and 60) ([Figure 3](#)).

Each subgroup from [Table 1](#) will be considered separately, and the tabular and graphical summaries described above will be replicated for each subgroup ([Table 10](#)). A forest plot will be generated to display 95% CIs for hazard ratios from each of the subgroup analyses ([Figure 7](#)).

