¹³ Steroids and other concomitant therapies intended as specific treatment of COVID-19, as well as all biologics, will be assessed from 7 days prior to enrollment to Day 29. All other concomitant medications will be assessed from 7 days prior to enrollment to Day 15 or upon discharge, whichever comes first.

¹⁴ Ordinal score only.

¹⁵ Vital signs include temperature, systolic blood pressure, heart rate, respiratory rate, O₂ saturation and level of consciousness. In addition, height and weight are obtained only at baseline (height can be self-reported). Vital signs collected as part of standard care may be used.

¹⁶ Day 1 is defined as the calendar day of randomization.

¹⁷ Blood draws for research labs may be omitted on any given study day if inappropriate for a subject's clinical status per site investigator judgment. In some instances, it may not be possible to collect blood for research laboratory investigations due to logistical reasons such as weekends or holidays or lack of necessary supplies. This will not constitute a deviation from the protocol.

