3. OBJECTIVES AND ENDPOINTS

Table 4. BET-B Study Objectives

OBJECTIVES	ENDPOINTS (OUTCOME MEASURES)
Primary	
To evaluate the clinical efficacy of lenzilumab as assessed by survival without mechanical ventilation through Day 29 in subjects with ordinal scores 5 or 6 at baseline with a CRP<150 mg/L and age<85 years.	Occurrence of mechanical ventilation or death at any point through Day 29 in subjects with ordinal scores 5 or 6 at baseline with a CRP<150 mg/L at baseline and age<85 years, where the event is one of these two categories: 7. Hospitalized, on invasive mechanical ventilation or extracorporeal membrane oxygenation (ECMO);

OBJECTIVES	ENDPOINTS (OUTCOME MEASURES)
	8. Death.
Key Secondary (in order of testing)*	

To evaluate the clinical efficacy of lenzilumab as assessed by:
 
 1. Survival without mechanical ventilation through Day 29 in subjects with ordinal scores 5 or 6 at baseline with a CRP<150 mg/L and age<85 years. 	
Time to ventilation or death Day 29 in subjects with ordinal scores 5 or 6 at baseline with a CRP<150 mg/L at baseline and age<85 years, where the event is one of these two categories:
 
 7. Hospitalized, on invasive mechanical ventilation or extracorporeal membrane oxygenation (ECMO); 8. Death.

 2. Time to sustained recovery compared to the control arm in subjects with ordinal scores 5 or 6 at baseline with a CRP<150 mg/L and age<85 years. 	
Day of recovery is defined as the first day on which the subject satisfies 1 of the following 3 categories from the ordinal scale (and does not return to a score of 4 or higher for the remainder of the study period):
 
 1. Not hospitalized, no new or increased** limitations on activities; 2. Not hospitalized, but new or increased limitation on activities and/or requiring new or increased home oxygen, CPAP, or BiPAP; 3. Hospitalized, not requiring new or increased supplemental oxygen - no longer requires ongoing medical care.

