### 3.2.2. Secondary Endpoints

1. Time to mechanical ventilation or death up to and including Study Day 29 for subjects < 85 years old with baseline ordinal score of 5 or 6 and baseline CRP < 150mg/L. That is time to a clinical status of:
  - Hospitalized, on invasive mechanical ventilation or ECMO (ordinal score 7); or
  - Death (ordinal score 8).
2. Time to sustained recovery as defined as the first day on which the subject who is < 85 years old with baseline ordinal score of 5 or 6 and baseline CRP < 150 mg/L satisfies 1 of the following 3 categories from the clinical status ordinal scale (and does not return to a score of  $\geq 4$  up to and including Study Day 60):
  - Not hospitalized, no new or increased limitations on activities (ordinal score 1);
  - Not hospitalized, but new or increased limitation on activities and/or requiring new or increased home oxygen, CPAP, or BiPAP (ordinal score 2);
  - Hospitalized, not requiring new or increased supplemental oxygen - no longer requires ongoing medical care (ordinal score 3).
3. Proportion of subjects at Day 29 that did not satisfy the following criteria up to and including Study Day 29:
  - For subject with baseline clinical status of 5 or 6:
    - Hospitalized, on invasive mechanical ventilation or ECMO (ordinal score 7);
    - Death (ordinal score 8); or
  - For subjects with baseline clinical status of 7:
    - Death (ordinal score 8).
4. Time to sustained recovery will be analyzed including all subjects randomized to BET-B including any shared controls from other stages.

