### 3.3. Study Definitions and Derived Variables

Refer to the master SAP for the definition of study day, analysis visit windows, and laboratory sample collection study day windows.

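### SAP 8.2.2 stops the recovery clock one day before recovery, while the protocol endpoint, the censoring rules and the sensitivity analysis use the actual day

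*SAP*

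**What the plan says.** Three places define the recovery endpoint.

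- Protocol Section 3, Table 4, for key secondary endpoints 2 and 4: "Day of recovery is defined as the first day on which the subject satisfies 1 of the following 3 categories from the ordinal scale".
- SAP 3.2.2, item 2: "Time to sustained recovery as defined as the first day on which the subject" reaches category 1, 2 or 3 without later worsening.
- SAP 8.2.2, the section that defines the analysis variable: elapsed days "from Study Day 1 to the day prior to the earliest recorded day at which a subject reaches recovery" and does not worsen through Day 60. It gives no reason for stopping a day early, and the SAP's summary of changes (Section 15) does not mention the rule.

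The neighbouring rules use actual days.

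- In the 8.2.2 primary analysis, subjects lost before recovery are "censored at the date of their last observed assessment, regardless of their discharge status".
- SAP Table 2 censors deaths before recovery at the expected Day 60.
- In the sensitivity analysis (8.2.2 and Table 2), subjects lost after discharge home count as recovered on the day of discharge or of the first score of 1 to 3, whichever is earlier.
- SAP 8.2.1 runs time to ventilation or death from Study Day 1 to the event date.
- SAP 8.2.4 sends the all-subject recovery analysis to Section 8.2.1, not 8.2.2.

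On counting, the protocol's schedule of assessments says "Day 1 is defined as the calendar day of randomization". SAP 3.3 says: "Refer to the master SAP for the definition of study day, analysis visit windows, and laboratory sample collection study day windows".

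**The concern.** The section that a programmer will follow does not derive the variable that the protocol names. It moves observed recoveries a day earlier and leaves every censoring time where it was. The medians, their confidence intervals, the Kaplan-Meier curve and the restricted mean recovery times for the primary subgroup (SAP Tables 10 and 12, Figure 3) would then describe a different quantity from the protocol endpoint.

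The sensitivity analysis would combine recoveries timed to the day before with recoveries timed to the day itself. Key secondary endpoints 2 and 4 could also be programmed on different clocks, because 8.2.4 points to a section without the day-before rule. This matters because time to sustained recovery is a key secondary endpoint, tested in the hierarchy of SAP 6.8.

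**Working it through.** The documents give no median, rate or power for time to recovery, so there is no stated figure to reproduce. The check has two parts: day arithmetic, then a simulation of how far the summaries move.

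**Day arithmetic.** Let *d* be the study day of first sustained recovery, with Day 1 the day of randomization.

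| Way of counting | To the first recovery day (protocol, SAP 3.2.2) | To the day before (SAP 8.2.2) | Censored on day *d*, or 8.2.1 event on day *d* |
|---|---|---|---|
| Date difference (Day 1 = 0) | *d* − 1 | *d* − 2 | *d* − 1 |
| Inclusive (Day 1 = 1) | *d* | *d* − 1 | *d* |
| Example *d* = 10, date difference | 9 | 8 | 9 |
| Example *d* = 10, inclusive | 10 | 9 | 10 |

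Within each row, 8.2.2 is one day below both the protocol endpoint and the censoring clock. Only by mixing rows do two entries agree: 8.2.2 counted inclusively equals the date difference to the first recovery day (both *d* − 1).

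A side effect follows. By date difference, a recovery on day *d* gets time *d* − 2, and so does a subject last seen unrecovered on day *d* − 1. With the usual rule that events precede censoring at ties, that subject is counted at risk for a recovery that happened after the last contact.

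**Simulation.** There were 400 subjects, 1:1, with 100 runs per setting. Event times were moved back one day and censoring times left alone. The following inputs are assumptions, not figures from the documents: control median of the recovery distribution 5, 8 or 15 days; recovery hazard ratio 1.25; 10% deaths, censored at Day 60; loss to follow-up 0%, 5% or 15%.

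| Loss to follow-up | Mean shift in median (days) | Mean shift in restricted mean (days) | Hazard ratio, day-before ÷ first-day, range over runs |
|---|---|---|---|
| 0% | −1.00 in every run | −0.84 to −0.90 | 1.000 |
| 5% | −1.00 in every run | −0.82 to −0.89 | 0.997 to 1.002 |
| 15% | −0.95 to −0.99 (single runs −1 to 0) | −0.80 to −0.87 | 0.995 to 1.005 |

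The mean change in the between-arm difference in medians was 0 to 0.02 day.

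The restricted-mean shift can be checked by hand. Without loss it is one day times the proportion with an observed recovery. With 10% deaths and a control median of 15 days, over 59 elapsed days this is 0.90 × (1 − 2^(−59/15)) = 0.90 × (1 − 0.0655) = 0.84, against 0.843 simulated.

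The hazard ratio hardly moves because subtracting one day from every event leaves the order of events unchanged. Only risk sets that contain subjects lost to follow-up can change.

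**The case against.** **The counting convention may remove the shift.** Protocol Table 4 and SAP 3.2.2 say which day is the recovery day, not how days are counted, and the study-day definition sits in the master SAP. If days are counted inclusively, the 8.2.2 rule gives the ordinary elapsed time to recovery. This stands as a limit on any absolute claim. It does not remove the inconsistency: under the same inclusive count, censoring and 8.2.1 events on day *d* get *d*, while a recovery on day *d* gets *d* − 1.

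**The ordinal score might describe the previous day.** The scale is defined in the Master protocol, so this cannot be excluded. But Protocol 8.1.2.1 has the score ideally taken just before study product is given, discharge has its own date, and a look-back would apply equally to score 7 in 8.2.1, where none is used.

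**The inference is unaffected.** This is correct. The offset is common to both arms.

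**A stronger reading.** A reader might infer that every reported recovery time and median is one day too short. The documents do not support that. Censored times do not move, the sensitivity analysis already uses the actual day for subjects lost after discharge, and 8.2.4 points to a section without the rule. Restricted means shift by less than a day. Nor can a percentage be given for this trial: one day is 20% of a 5-day median, 12.5% of 8 and 6.7% of 15, and the documents do not say which applies. The protocol's figure of about 75% discharged by Day 8 comes from the LIVE-AIR subgroup.

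**Conclusion.** The contradiction is real and lies within the SAP as well as between SAP and protocol. Counted one way throughout, each observed recovery in the 8.2.2 primary analysis is one day shorter than the protocol endpoint, and events and censoring are on different clocks. The Kaplan-Meier median normally shifts by one day and the restricted mean by about 0.8 to 0.9 day; the curve for observed recoveries shifts accordingly. The simulated sizes rest on the assumed recovery, death and loss rates. The one-day offset per observed recovery does not. Whether the published median would be short in absolute terms depends on the master SAP's study-day convention, which is not available here.

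The hazard ratio, the test and the between-arm difference in medians are essentially unchanged. This should be corrected so that the descriptive results match the endpoint and two programmers would derive the same variable. It does not threaten the conclusion of the test.

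**What to change.** - In SAP 8.2.2, run the time to the first day of sustained recovery, as in Protocol Table 4 and SAP 3.2.2.
- State the day count once, for example date of first sustained-recovery day minus date of Study Day 1, with or without adding one. Changing the end day without stating the count would leave the ambiguity in place.
- Apply that count to observed recoveries, censoring at last assessment, censoring of deaths at Day 60, and recoveries assigned in the sensitivity analysis (8.2.2 and Table 2).
- In SAP 8.2.4, change the cross-reference from 8.2.1 to 8.2.2.
- If the master documents contain a reason for the day-before rule, cite it and explain how events and censoring are then aligned.

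The cost is a few sentences of SAP text and one derivation line. No data collection, sample size or alpha changes.

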### **8.2.3. Survival without Mechanical Ventilation up to and Including Day 29 for All Subjects in the ITT and mITT Populations**

The analysis for survival without mechanical ventilation for the primary endpoint described in Section 8.1 will be repeated for all subjects in the ITT population without the restrictions in [Table 5](#) and all subjects in mITT population in [Table 6](#).

### **8.2.4. Time to Sustained Recovery up to and including Day 60 for ITT Population**

The analysis for the time to sustained recovery for the primary endpoint subgroup described in Section 8.2.1 will be repeated for all subjects in the ITT population without the restrictions. Results will be reported in [Table 11](#), [Table 12](#), [Figure 4](#), and [Figure 8](#).

## **8.3. Other Secondary Efficacy Analyses**

The analysis described for the other secondary efficacy and safety endpoints in the Master SAP will be followed. However, analysis of secondary endpoints will be conducted for all subjects in the ITT Population and only 95% confidence intervals will be reported for efficacy and safety analyses. For the time to death and mortality endpoints, additional tables for the primary subgroup and full ITT population will be provided in [Table 13](#) and [Table 14](#), respectively. Results for time to death and mortality using subjects with baseline ordinal score of 5 or 6, CRP $\geq$ 150 mg/L, and age $<$ 85 years are provided in [Table 15](#). Results from analysis of time to death using a restricted mean survival approach are provided in [Table 16](#).

## **9. SAFETY EVALUATION**

Safety evaluation for this study will be similar to that provided in the master SAP. However, additional safety summaries by baseline CRP<150 and CRP≥150 will be provided.

### **9.1. Demographic and Other Baseline Characteristics**

Refer to Section 9.1 of the master SAP.

### **9.2. Measurements of Treatment Compliance**

Refer to Section 9.2 of the master SAP.

### **9.3. Adverse Events**

Refer to Section 9.3 of the master SAP.

### **9.4. Deaths, Serious Adverse Events and other Significant Adverse Events**

Refer to Section 9.4 of the master SAP.

